4. OBJECTIVES AND OUTCOME MEASURES/ENDPOINTS

Hypothesis: Compared to standard care, administering patiromer to patients who have worsening congestion due to heart failure and hyperkalaemia (defined as a serum potassium >5.0mmol/L) allows use of higher doses of mineralocorticoid receptor antagonists (MRA) thereby improving congestion and reducing cardiovascular morbidity and mortality.

4.1 Primary Objective

To find out whether patients with worsening congestion due to heart failure and hyperkalaemia who are randomised to patiromer (thus enabling the use of higher doses of MRA) have a lower rate of

Version 5.0 22 July 2021 Page 20 of 82

worsening heart failure [defined as a composite of need for parenteral diuretic therapy (either intravenous [IV] or subcutaneous [SC]) for worsening or recalcitrant heart failure (subsequent to discharge from index episode of care), re-hospitalisation for worsening heart failure or non-cancer mortality] compared to patients assigned to a control group that does not receive patiromer.

4.2 Other Primary Objectives

For the Registry

To investigate the willingness of patients with worsening heart failure who require higher doses of diuretics to control worsening symptoms and signs of congestion to participate in a research registry and/or, in principle, a randomised trial (not necessarily this particular trial). Participants may or may not satisfy the criteria for enrolment in the RELIEHF randomised trial. Registry participants will be followed up only through their electronic health records to assess mortality and morbidity. No further research visits are required.

For the Randomised Trial until Day 60

To find out whether administering patiromer and higher-dose MRA improves evidence of congestion on Day 60 (±10 days) compared to standard care.

4.3 Secondary Objectives

For the Registry

To describe the characteristics and outcome of patients with worsening heart failure who require higher doses of diuretics to control worsening symptoms and signs of congestion.

For the Randomised Trial until Day 60

To find out whether patients with worsening congestion due to heart failure and hyperkalaemia who are randomised to patiromer receive higher doses of MRA and have less severe symptoms and signs of congestion, quality of life and hospital length of stay compared to patients assigned to those who are randomised to standard care.

Randomised Trial (long-term follow-up)

To find out whether patients with worsening congestion due to heart failure and hyperkalaemia who are randomised to patiromer receive higher doses of MRA, have improved long-term quality of life, spend less time in hospital and have lower all-cause mortality compared to patients assigned to standard care.

4.4 Outcome Measures/Endpoints

Endpoints have been chosen to reflect the clinical aims of managing patients with worsening congestion due to heart failure. The 'narrative' is that better management of congestion by patiromerfacilitated, dose-escalation of MRA will improve symptoms and signs of congestion, leading to a shorter hospital stay, improved quality of life, less need for intravenous and intensified oral diuretic therapy, fewer readmissions for worsening heart failure and increased longevity.

4.5 Primary Endpoint

Composite of time to need for IV or SC diuretics for worsening or recalcitrant heart failure (subsequent to discharge from index episode of care), (re-)hospitalisation for worsening heart failure or non-cancer

Version 5.0 22 July 2021 Page 21 of 82

deaths. The trial is powered on time-to-first event but analysis will include first and recurrent events for the primary endpoint.

4.6 Other Primary Endpoints

For The Registry

Time to first (re-)hospitalisation or death

Randomised Trial until Day 60

- Congestion Index on Day 60, comprising changes from baseline in
 - i. Weight
 - ii. Severity of peripheral pitting oedema
 - iii. Breathlessness symptom score
 - iv. Dose of loop and thiazide diuretics
 - v. Walk Test Time (will be considered zero at baseline if not available)
 - vi. Plasma concentration of NT-proBNP
 - vii. Plasma concentration of CA125

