4.7 Secondary Endpoints

Registry

- Time to first cardiovascular (re-)hospitalisation or non-cancer death as judged by primary and secondary ICD-10 codes
- Time to first heart failure (re-)hospitalisation or non-cancer death as judged by primary and secondary ICD-10 codes
- Incidence-rate for hospitalisation, all-causes and due separately to cardiovascular causes, heart failure or cancer, and other as judged by primary and secondary ICD-10 codes
- Time to death
 - All-cause and due to cardiovascular, heart failure, cancer and other based on hospitalisation data and death certificates.

The data for all registry outcome events will be obtained solely by linkage to electronic medical records.

Randomised Trial until Day 60

- Dose of MRA (Days 7 & 60)
- Congestion Index (Days 7& 60)
- Days dead or hospitalised during the first 60 days
- Individual Components of the Congestion Index (Days 7 &60)
- Quality of Life at (Days 7 &60)
- NYHA class (Days 7 &60)
- Patient Global Assessment (PGA) (Days 7 &60)

Randomised Trial (long-term follow-up)

- Mortality
 - All-Cause
 - Non-Cancer

- Cardiovascular
- Days lost to hospitalisation for heart failure or non-cancer mortality over 12 months
- Days lost to any hospitalisation or death over 12 months
- Quality adjusted life-years for the duration of the trial using EQ5D
- Proportion alive & well at 12 months (well-being defined by KCCQ quality of life score)
- Dose of MRA taken at the time of the 6 and 12 month visits
- Dose of oral diuretics other than MRA taken at the time of the 6 and 12 month visits
- NYHA class at 6 and 12 months
- Patient Global Assessment (PGA) at 6 and 12 months

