^{-00 =} screening log; -0 = consented registry; 0 = consent for trial; RI = run-in phase awaiting rise in potassium. κ = randomisation. T = titration visit. Day 7* = day 7 or discharge if sooner. EOS = end of trial. CV = cardiovascular. X* vital signs measured during orthopnoea (orthop) test. Opt = optional

Local Haematology = Haemoglobin, Haematocrit, White Cell Count, Neutrophils, Lymphocytes.

Local Biochemistry = Sodium, Potassium, Urea, Creatinine.

Local Biochemistry+ = Sodium, Potassium, Magnesium, Bicarbonate, Calcium, Phosphate, Urea, Creatinine, Bilirubin, Transaminases, Alkaline Phosphate, Albumin.

KCCQ = Kansas City Cardiomyopathy Questionnaire. EQ5D = EuroQol 5-dimension questionnaire. NYHA = New York Heart Association functional class. PGA = patient global assessment on a 7-point scale ranging from much worse to much better.

[@] for patients who feel unable to do these tests, the reason will be recorded. AE / SAE = adverse / serious adverse events.

[♦] includes vaccine history

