8.7 Data Collection

MR = from **M**edical **R**ecords. If not in the existing record, variables will be recorded as "not available" X = a test, measurement or question that research staff will do/ask if not in the existing medical record; MR/X = either approach to obtaining data is possible; shaded cells = data not collected in this period. To be read in conjunction with schedule of assessments and narrative subsequent to this table.

-			rrative subsequent to this table. Randomised Trial				
	Screening Log #	Registry	Baseline	60 Day	Long- Term		
Fulfil Entry Criteria	MR	MR	MR/X				
Willingness to Participate in Research	X	X					
Year of Birth	MR						
Date of Birth		MR					
Sex	MR						
Ethnicity		MR/X					
Smoking History		MR/X					
Alcohol Intake		MR/X					
Contact Details		MR/X					
Hospitalisation Status	MR	MR/X	MR/X				
Aetiology	MR	MR/X					
Co-morbidity		MR/X					
Duration of Heart Failure	MI	R/X					
Causes of Worsening		MR/X					
Frailty Score	X	(X)					
Symptom Severity		X	Х	Х	X		
NYHA Class		Х	Х	Х	X		
PGA			Х	Х	X		
CV Therapy	MR (limited)	MR/X	MR/X	MR/X	MR/X		
Non-CV Therapy		MR/X	MR/X	MR/X	MR/X		
Height	MR	X	X	X			
Weight	MR	X	X	X	X		
Vital Signs	MR (limited)	X	X	X	X		
Physical Exam		X	X	X	X		
Orthopnoea Test #		X	X	X	X		
ECG		MR/X	X	X	X		
Echocardiogram or	N	IR	MR/X		7.		
other imaging test		time)	(in prior 3 yrs)				
Haematology	()	MR	MR/X	MR/X	MR/X		
Biochemistry	MR Sodium Potassium Creatinine	MR • Full Panel	MR/X	MR/X	MR/X		
Snot Urino	Urea	MR	X	X	X		
Spot Urine Biomarkers		X (optional)	X	X	X		
		A (optional)	^	^	^		
(Core Lab)		V (ontional)	v	X	X		
KCCQ		X (optional)	X	X	X		
EQ5D		X (optional)					
10 metre Walk Test		X (optional)	X	X	X		
Events & SAE			X	X	X		

[#] See HRA guidance in section 7.1.1.

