- The following if done in the previous two years only (low availability anticipated)
 - o Plasma Brain Natriuretic Peptide (BNP) or NT-proBNP
 - o Serum iron, transferrin saturation, ferritin
 - Urine for albumin/creatinine ratio

Echocardiogram (most recent test)

- Test Available Yes/No
 - o If yes, date
- Left Ventricular Function
 - Left ventricular ejection fraction (provide value; may be done by an alternative imaging method for instance nuclear scan, magnetic resonance imaging or computed tomography)
 and/or
 - Systolic Dysfunction None, Mild, Moderate, Severe, Don't Know and/or
 - HFrEF, HFmrEF, HFpEF or Don't Know
- Left Atrial Enlargement
 - None, Mild, Moderate, Severe, Don't Know
- **Valve Disease**(may also be assessed by magnetic resonance imaging)
 - Mitral Regurgitation (none / mild / mod. / severe / or state "not available")
 - Aortic Stenosis (none / mild / mod. / severe / or state "not available")
 - Tricuspid Regurgitation (none / mild / mod. / severe / or state "not available")
 - Other valve disease (none / mild / mod. / severe / or state "not available")
- Dimensions
 - LV end-diastolic
 - Left atrial dimension
- Please provide video (optional)

The Following Questionnaires and Sets of Tests are Optional for The Registry

Physical Examination

An appropriately trained health professional should measure these. If an appropriately qualified person is not available, then this unavailability should be recorded.

- Jugular Venous Pressure (optional for registry)
 - Not visible, Normal (<4cm above sternal angle), Raised 4-10cm above sternal angle, Raised >10cm above sternal angle
- 3rd Heart Sound (optional for registry)
 - o Present / Absent
- Lung crepitations (optional for registry)
 - o Absent, Unilateral, Bilateral Basal, Bilateral to Mid-Zone, All Lung-Fields
- Hepatomegaly
 - o Present / Absent

Biomarkers

- 10mL of blood taken into EDTA tubes (see laboratory manual for preparation and transport to core laboratory).
- Sample taken (Yes/No)
- If Yes, barcode

Quality of Life Assessment

- EQ5D
- Kansas City Cardiomyopathy Questionnaire (KCCQ)

Electrocardiogram (ECG)

Transmit 12-lead electrocardiogram electronically.

10 metre Walk Test (in triplicate) https://www.physio-pedia.com/10 Metre Walk Test

- Attempted (Yes/No/ If no, provide reason (many will be unable to attempt this at baseline)
- Not attempted (reasons)–

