 - patient feels unable due to a) breathlessness, b) fatigue, c) joint or muscle pains d) dizziness / instability e) not ambulatory (more than one may apply)
 - · Patient feels able but unwilling
 - Insufficient investigator a) time, b) space, c) both
 - Duration
 - 1st Attempt (seconds)
 - 2nd Attempt (seconds)
 - o 3rd Attempt (seconds)
 - After final test (this may be after one, two or three tests)
 - o Breathlessness rating, Fatigue rating, Respiratory rate, Heart rate

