8.7.3 Clinical Trial

Raseline

Data gathered for the registry may be used as the baseline data for the randomised trial providing the dates are the same. If the dates differ, tests as shown in the schedule of assessments should be repeated. In addition, the following tests and measurements are mandatory prior to randomisation:

- 1. Blood collection for biomarkers
- 2. EQ5D and KCCQ questionnaires
- 3. Walk Tests
- **4.** Electronic transmission of the ECG: record and transmit 12-lead ECG to the Glasgow electrocardiology core laboratory. ECGs will be identified only by participant registration number.

Follow-up

Assessments will be repeated as at baseline on Days 7 and 60 and at 6, 12 and 24 months.

For safety visits (in addition to those above), vital signs consist only of measurements of heart rate, blood pressure and oedema grade and for biochemistry only includes sodium, potassium, urea and creatinine.

A Patient Global Assessment (PGA) which assesses the change compared to baseline will also be done at each follow-up visit as an assessment of symptoms.

Trial assessments

There will be two types of clinical assessments in this trial

a) Assessments for Efficacy at 7 and 60 days and at 6, 12 and 24 months

b) Assessments for Safety at 1, 3, 5, 14, 30days and at 3, 9, 15, 18, 21, 27 months and every 3 months thereafter until the end of the trial.

Visits for assessment of efficacy require all baseline assessments to be repeated with the exception of demography and prior medical history. Echocardiography is optional.

Visits for assessment of safety require evaluation only of symptoms, weight, concomitant cardiovascular therapy, severity of oedema, blood pressure and a blood test for measurement of serum sodium, potassium, urea and creatinine.

Longer-term efficacy and safety during the randomised trial will be assessed by reports of adverse reactions, serious adverse events and the primary composite endpoint and its components.

Participants should be encouraged at each visit to bring any remaining trial medicines (patiromer/spironolactone or eplerenone). An assessment of compliance will be made at each trial visit by research staff and documented in the eCRF. Unused IMP should be returned to the site pharmacy where it will be logged and disposed of safely.

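### Setting an unavailable baseline walk time to 0 seconds would make a patient who regains walking look slower on the walk component of the Day-60 Congestion Index, if change in seconds is used as written

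*Protocol*

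**What the plan says.** Protocol 4.6 makes the Congestion Index the other primary endpoint of the randomised trial to Day 60. It is made up of changes from baseline in seven components, the fifth being "Walk Test Time (will be considered zero at baseline if not available". Protocol 4.7 also makes each component a secondary endpoint: "Individual Components of the Congestion Index (Days 7 &60").

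The table in Protocol 8.7 names one walk test, the "10 metre Walk Test". Protocol 8.7.2 (Consented Registry) asks for up to three attempts, each recorded as a duration, for example "1st Attempt (seconds").

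On availability, the documents say three things:

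- Protocol 8.7.3 includes walk tests where it says "the following tests and measurements are mandatory prior to randomisation".
- The footnote to the schedule in 8.1.1 nevertheless provides that "for patients who feel unable to do these tests, the reason will be recorded".
- Protocol 8.7.2 remarks that "many will be unable to attempt this at baseline". It lists reasons for not attempting the test. These include inability from breathlessness, fatigue, pain or dizziness, but also unwillingness in a patient who feels able, and "Insufficient investigator a) time, b) space, c) both".

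Neither document converts time to speed, gives a direction or weights for the seven components, or gives a value for a walk test that cannot be done at Day 7 or Day 60. Protocol 11.3 analyses congestion scores by t-test without imputation. Protocol 11.7 analyses continuous variables with and without imputation. SAP 1.6.1 and 1.6.3 report that the trial closed with 4 participants randomised and that no formal analysis will be done. SAP 2.6 lists the walk test by visit, and the Congestion Index is not among its items.

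**The concern.** Over a fixed distance a shorter time is a better result. Zero seconds is therefore not a neutral placeholder or a poor score: it is faster than any real walk. Any completed follow-up walk after a zero baseline counts as an increase in time, that is, as deterioration. The patients affected include those who were too breathless or tired to walk and can now do so, which is the improvement that the index is meant to detect.

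By design the component matters in three places: as a secondary endpoint at Days 7 and 60, as one seventh of the list that forms the Day-60 other primary endpoint, and, through the overall index, in the lack-of-improvement criterion of Protocol 11.5.

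**Working it through.** **The plan's own figure.** The only figure given for the index is more than 90% power with 400 patients at 0.325 SD (Protocol 11.1). With 200 per arm and two-sided 5% (the alpha is not stated, so this is assumed), power = Φ(0.325 × √(200/2) − 1.96) = Φ(1.29) = 0.90. It reproduces, but it is stated in SD units of an undefined score and has no bearing on this point.

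**Sign check.** Change = follow-up time − baseline time, in seconds, with baseline = 0 if unavailable. The times are illustrative.

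| Patient | Baseline | Day 60 | Change | True course |
|---|---|---|---|---|
| A, measured twice | 30 s | 18 s | −12 s | faster |
| B, unable at baseline | set to 0 s | 18 s | +18 s | regained walking |
| C, measured twice | 12 s | 20 s | +8 s | slower |
| D, unable at baseline | set to 0 s | 20 s | +20 s | regained walking |
| E, able, but no staff time at baseline | set to 0 s (true 20 s) | 20 s | +20 s | unchanged |

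D scores worse than C, who really slowed. If the sign is reversed so that a longer time is better, B and D come right but A is scored as worse and C as better. No single direction suits both groups. E shows that the rule also distorts the score of patients who could already walk.

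On a speed scale (10 m divided by time, 0 m/s for inability) the directions agree: B gains 10/18 = 0.56 m/s, D gains 10/20 = 0.50 m/s, A gains 10/18 − 10/30 = 0.22 m/s, and C loses 10/12 − 10/20 = 0.33 m/s.

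**Effect on a group comparison (illustration only; every input is assumed).** Let u be the share unable at baseline, the same in both arms because it is fixed before randomisation. Let r be the share of these who walk at follow-up, T their mean time, and d the mean improvement of measured walkers. Those still unable at Day 60 drop out. The recovered share of those analysed is p = ur / (1 − u + ur), and

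- mean change = −(1 − p)d + pT
- variance = (1 − p)·3² + p·5² + p(1 − p)(T + d)²

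with SD 3 s for walkers and 5 s for recovered patients. Take T = 18 s, control d = 2 s and r = 50%, patiromer d = 3 s.

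*Equal recovery, u = 10%.* p = 0.05/0.95 = 0.053 in both arms. The mean changes are −0.95 s and −1.89 s, a difference of −0.95 s. The variances are 29.8 and 31.8, so the pooled SD is 5.55 s. The benefit is 0.17 SD, against 1/3 = 0.33 SD with nobody unable. The difference in means hardly moves; most of the loss comes from the inflated variance.

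*Patiromer recovery 65%, u = 10%.* Patiromer p = 0.065/0.965 = 0.067 and its mean change is −1.59 s. The difference is −0.64 s and the pooled SD is 5.81 s, so the benefit is 0.11 SD.

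| Patiromer recovery | u = 0 | 10% | 20% | 40% |
|---|---|---|---|---|
| 50% (equal) | 0.33 | 0.17 | 0.12 | 0.08 |
| 60% | 0.33 | 0.13 | 0.06 | 0.00 |
| 65% | 0.33 | 0.11 | 0.04 | −0.04 |

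Entries are the apparent patiromer benefit on the walk component in SD. The sign changes at u = 40% for 60% recovery and at about 29% for 65% recovery. It does not change with equal recovery.

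**The case against.** The strongest case on the other side has four parts.

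1. **No scoring is given.** A banded or ranked score might have treated zero as a code for a test not done, and Protocol 11.8 leaves full detail to a SAP for each phase. This stands as a limit: the error is conditional on change in seconds being used as written. It does not remove the point, because 4.6 specifies a change in time and supplies the number zero, and the SAP does not alter it.

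2. **Few randomised patients may be affected.** Walk tests are mandatory before randomisation, and the remark that many will be unable sits in the registry section. A reader might infer that many randomised patients would get a zero baseline. The documents do not support that: they give no share, and a run-in of up to 35 days may separate registry entry from randomisation. They do not rule it out either, since 4.6 and the footnote in 8.1.1 both provide for an unavailable test.

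3. **Bias against patiromer is not shown.** A reader might infer that the rule reverses the treatment effect or biases the Day-60 index against patiromer. The documents do not support that either. Availability at baseline is balanced in expectation, and with equal recovery the rule only dilutes. Reversal needs both a difference in recovery and a large share unable, and the documents give neither. Without weights nothing can be said about the size of the effect on the total index.

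4. **Nothing reported changes.** This is correct and settles the severity.

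An objection to the remedy also stands. Scoring inability as worst at follow-up is a rule for tests not performed, and it has to be squared with Protocol 11.3 and 11.7. Inability from joint pain or dizziness is also not obviously congestion.

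**Conclusion.** The zero-time rule in Protocol 4.6 is wrong as written. This is a stated rule that points the wrong way, not a missing detail, and nothing elsewhere in the protocol or the SAP repairs it. The conclusion needs only three facts from the documents: a fixed 10 m distance, a result in seconds, and change from baseline. The assumed figures above show how dilution and reversal could arise; they are not estimates for this trial.

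The severity is minor. The point is confined to the definition of one component, the number of patients affected is unknown, and with listings for 4 randomised participants no result depends on it. It would matter if the index were reused elsewhere with this rule.

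**What to change.** - In Protocol 4.6, delete the zero-time rule. Score the component on a scale where recorded inability is the worst value, for example speed (10 m divided by time) with 0 m/s for inability, or a worst rank.
- Treat tests not done for non-clinical reasons (able but unwilling, insufficient investigator time or space) as missing. State how inability from pain or dizziness is classed.
- If inability is also scored at Day 7 and Day 60, reconcile this with the no-imputation rule in 11.3 and with 11.7.
- If any change in walk time is derived from the existing data, do not apply the zero rule. With the trial closed, this is the only step that can still affect reporting.

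**Cost.** Small wording changes in 4.6 and in 11.3 and 11.7. No new data are needed, because times and reasons for not testing are already recorded. Speed may be slightly less sensitive than raw time in patients measured at both visits: 0.26 SD against 0.33 SD with nobody unable, on assumed inputs (those above, plus a baseline of 15 s with SD 5 s). A speed scale restores the direction but does not by itself prevent dilution: on the same assumptions with equal recovery, the benefit falls from 0.26 SD to 0.20 SD at 20% unable.

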4.7 Secondary Endpoints

Registry

- Time to first cardiovascular (re-)hospitalisation or non-cancer death as judged by primary and secondary ICD-10 codes
- Time to first heart failure (re-)hospitalisation or non-cancer death as judged by primary and secondary ICD-10 codes
- Incidence-rate for hospitalisation, all-causes and due separately to cardiovascular causes, heart failure or cancer, and other as judged by primary and secondary ICD-10 codes
- Time to death
 - All-cause and due to cardiovascular, heart failure, cancer and other based on hospitalisation data and death certificates.

The data for all registry outcome events will be obtained solely by linkage to electronic medical records.

Randomised Trial until Day 60

- Dose of MRA (Days 7 & 60)
- Congestion Index (Days 7& 60)
- Days dead or hospitalised during the first 60 days
- Individual Components of the Congestion Index (Days 7 &60)
- Quality of Life at (Days 7 &60)
- NYHA class (Days 7 &60)
- Patient Global Assessment (PGA) (Days 7 &60)

Randomised Trial (long-term follow-up)

- Mortality
 - All-Cause
 - Non-Cancer

- Cardiovascular
- Days lost to hospitalisation for heart failure or non-cancer mortality over 12 months
- Days lost to any hospitalisation or death over 12 months
- Quality adjusted life-years for the duration of the trial using EQ5D
- Proportion alive & well at 12 months (well-being defined by KCCQ quality of life score)
- Dose of MRA taken at the time of the 6 and 12 month visits
- Dose of oral diuretics other than MRA taken at the time of the 6 and 12 month visits
- NYHA class at 6 and 12 months
- Patient Global Assessment (PGA) at 6 and 12 months

